1 PROTOCOL SUMMARY

1.1 SYNOPSIS

Title:	Outreach-ER: A Dementia Care Intervention Program
IRB Number:	A# 22-086
Study Description:	This is a feasibility/pilot, prospective cohort study to determine how to implement and refine Outreach-ER intervention for a larger clinical study. A key feature of Outreach-ER is to reach out to PLWD and their families following an emergency room visit or hospitalization. The outcome of this study will help in the overall goal of studying the impact of Outreach-ER in a larger clinical study and focus on outcomes relevant to PLWD and their care partners.
Specific Aims and Outcomes:	
Aim 1: To assess the feasibility and acceptability of Outreach-ER. This aim will be accomplished by collecting detailed process data which will allow the assessment of registration, enrollment, retention, and adherence/fidelity to the program
 
Aim 2: To assess feasibility of collecting outcomes and explore the effectiveness of Outreach-ER. In care partners, we will evaluate the pre-post benefits of Outreach-ER to improve mood (Center for Epidemiologic Studies Depression Scale-10), reduce burden (Zarit Burden Interview-12), reduce stress (Perceived Stress Scale) and improve quality of life. We will describe and report healthcare utilization in PLWD, such as 30-day hospital readmissions and number of emergency room visits.

Study Population:	
Inclusion Criteria
 
• PLWD with a recent Emergency department visit or admission at Regions Hospital or Methodist Hospital• Diagnosis of dementia based on ICD Codes in the medical record• Provides informed consent prior to participation• Must be able to read and speak English• PLWD Living at Home• Age >=18 years for PLWD and their care partner 
Exclusion
 
• PLWD living in a nursing home/Long term care – Assisted living facility• Current involvement in another clinical research study/trial for care partners• PLWD MRN on the HP exclusion list
Description of Sites/Facilities Enrolling Participants:	Sample Size: We plan to enroll 30 PLWD and their families.
Study Duration:	Participants will be enrolled at HealthPartners Neuroscience Center, located at [name].
Participant Duration:	The duration of this study is 1.5 years.
	Participants are in the study for 5-6 months

1.2 SCHEMA

2 INTRODUCTION

2.1 BACKGROUND & STUDY RATIONALE

Alzheimer's disease affects 6.2 million individuals in the United States and results in an annual cost of care of \$355 billion, including \$239 billion in Medicare and Medicaid payments combined ("2021 Alzheimer's disease facts and figures," 2021). People living with dementia (PLWD) often receive poorly coordinated and fragmented care that can lead to ineffective care and poor health outcomes, including trips to the emergency department and hospitalizations (Hirschman & Hodgson, 2018). Care for PLWD is demanding and stressful, as the needs of those with dementia are constantly evolving as their behavior and abilities change. Caregivers often experience mental health concerns such as anxiety and depression, poor physical health, compromised immune system, and emotional and social issues due to the demands and stress of caregiving (Elliott, Burgio, & DeCoster, 2010; Ferrara et al., 2008).

Multicomponent non-pharmacological psychosocial care interventions such as REACH (Resources for Enhancing Alzheimer's Caregiver Health), or NYUCI (NYU Caregiver Intervention) include more than one care technique or delivery method to foster support, expertise, information, or skills for caregivers to improve caregiver quality of life and health outcomes. These interventions usually include therapy and social support, education, supportive feedback, goal setting, and planning, as well as relaxation and physical exercises. These are offered as structured approaches to develop skills for problem solving, improving communication and improve relationships for caregivers and PLWD. These approaches have been recognized as high priority in the Alzheimer's research community to study the real-world effectiveness and implementation across different health care settings (Larson & Stroud, 2021). The multicomponent interventions such as REACH, NYUCI have been shown to reduce stress, improve depression, well-being of caregivers and delays nursing home placement of PLWD (OUT, 2018). Key challenges to these interventions include implementation, identifying & tailoring interventions to specific level of dementia and care partner support, and efficacy of caregiver-related interventions (Gaugler, Jutkowitz, & Gitlin, 2020; Hodgson & Gitlin, 2021). REACH-TX was effective in improving quality of life and decreasing caregiver burden when administered by a community agency, as there were

significant statistical improvements from baseline to 6 months on quality of life for caregivers (Cho, Luk-Jones, & Stevens, 2018). NYUCI has also been modified to provide support to different caregivers including adult children and families and has shown similar improvement in caregiver outcomes (Sperling et al., 2020). In Minnesota, there is currently a study in progress to adapt this intervention to be delivered in combination with adult day services (Gitlin et al., 2019). A key missing element in these clinical trials was that PLWD who have had multiple recent emergency visits or hospitalizations were excluded. In this proposed study we are utilizing a psychosocial interventional approach like REACH and NYUCI with a focus on PLWD with recent ER visits or hospitalizations and their care partners, as the needs and burden are different (Benner, Steiner, & Pierce, 2018).

Multicomponent intervention-based studies have focused on caregiver outcomes and have specifically not examined the effects on PLWD healthcare utilization outcomes. Individuals with dementia are more often hospitalized than those without dementia. In many cases, these hospitalizations are avoidable (Phelan, Borson, Grothaus, Balch, & Larson, 2012). In 2013, 21% of hospitalizations for fee-for-service Medicare enrollees with Alzheimer's or dementia were either unplanned readmissions within 30 days of prior hospitalization, or an ambulatory care visit for a condition that was potentially avoidable with effective outpatient care ("2021 Alzheimer's disease facts and figures," 2021). Studies suggest that caregiver burden and stress may be associated with healthcare utilization of PLWD (Guterman et al., 2019; Lau et al., 2021). In a cross-sectional survey with 399 PLWD and their caregivers, caregiver distress from behavioral and psychological symptoms (BPSD) was positively associated with emergency room utilization, while caregiver burden was positively associated with length of hospital stay (Lau et al., 2021).

We propose to study a new care intervention called Outreach-ER. A key feature of Outreach-ER is to reach out to PLWD and their families following an emergency room visit or hospitalization. In this study, we will assess the feasibility of identifying and recruiting PLWD and their families and collect health-related outcomes to explore its effectiveness. The outcome of this study will help in the overall goal of studying the impact of Outreach-ER in a larger clinical study and focus on outcomes relevant to PLWD and their care partners.

2.2 RISK/BENEFIT ASSESSMENT

2.2.1 KNOWN POTENTIAL RISKS

There are minimal risks associated with participation in this study

Survey and Assessments

The questions on these assessments may make participants feel uncomfortable because some parts may be easy to answer, while some parts may be difficult or tiring. It may also cause individuals to feel uncomfortable or upset. The health history survey probes for personal health history information that may be sensitive information. Participants may skip any questions that make them feel uncomfortable.

One risk is that participants may experience discomfort or fatigue in having research staff call or visits to your home.

Loss of Confidentiality

There may be a slight possibility of breach of confidential information that was collected. However, the following procedures will be implemented to reduce this risk:

- Data collection and reporting tools will be developed and stored internally.
- Data collected and stored electronically will remain confidential and secure (e.g. secured server and password protected files [REDCap]).
- Study binders will be stored in a locked file cabinet within a locked office.
- After the study is closed, all subject identifiers will be destroyed.

2.2.2 KNOWN POTENTIAL BENEFITS

Participants may or may not benefit from this study. Similar interventions have shown benefits with regard to care partner outcomes such as reducing burden, improving mood and reducing stress. The participants will receive the written care plan from experts. The results of this may aid in future clinical research studies for care intervention programs for People living with Dementia and their families.

2.2.3 ASSESSMENT OF POTENTIAL RISKS AND BENEFITS

We believe the potential risks to the participants in this study are minimal.

The following measures will be taken to protect providers and patients from the risk of breach of confidentiality:

- A unique study ID code unrelated to the medical record number or other study subject-specific information will be assigned to each patient and used to link data from various sources and needed for analysis. The study number will be used on the RedCap database.
- All field notes and assessment data from the consultants will be uploaded/transcribed in REDcap.

3 OBJECTIVES AND ENDPOINTS

Aim 1: To assess the feasibility and acceptability of Outreach-ER.

• Recruitment rate• Participation rate• Completion rate• Session completion rate• Questionnaire specific response rate
Aim 2:
Care Partners

• Rate of completion for all scales• Exploratory- effectiveness
PLWD

• 30-day hospital readmission rate

- Number of ED visits in 6 months before and 3-month period following the intervention
- Number of ED to Hospital admission in 6 months before and 3-month period following the intervention
- Number of Clinic visits (planned/unplanned) 6 months before and in a 3-month period following the intervention

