5.5 STRATEGIES FOR RECRUITMENT AND RETENTION

Recruitment: A recruitment letter and flyer will be sent out to patients identified as eligible. Within a few days after discharge (2 days to 2 weeks) research staff will reach out to patients and their caregivers via a phone call. If interested, the caregiver and patient will be provided with informed consent to review on their own time. A video or phone encounter will be arranged to provide additional details of the study and informed consent. Participating subjects will need to explain in their own words what the study entails. A virtual consent through REDcap or a mailed consent with witness will be obtained.

Remuneration: Participants will be provided gift cards totaling \$100 per dyad for completing certain visits of the research study.

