7.3 INTERVENTION VISITS

7.3.1 VISIT 3 (WITHIN 3 MONTHS OF DISCHARGE FROM HOSPITAL)

- This visit may be a telephone/video visit
- Initial visit by Amplio consultants
- Setup intervention visits schedules
- This visit is about 15 minutes.

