9 STATISTICAL CONSIDERATIONS

9.1 STATISTICAL ANALYSIS PLAN

Aim 1: To assess the feasibility, acceptability, and fidelity of implementation of the Outreach-ER program we will begin by measuring the absolute number of potential care dyads of care partners (CP) and PLWD contacted for recruitment and the number of those who consent and enroll. These will be used to calculate the overall rate of program registration. The feasibility of collecting CP provided data will be evaluated by quantifying the missingness in the registration materials as well the response rate to the two questionnaires. Fidelity of the intervention will be assessed by describing CP attendance rates, length of intervention, and number of sessions as recorded by Outreach-ER staff. Completion patterns will be summarized overall and stratified by patient demographics. Any differences in intervention fidelity associated with CP and PLWD demographics will be described and discussed. Acceptability of the intervention will be assessed using data gathered through the post-intervention interview. The interviews will be transcribed, and recurring themes will be identified by the study team. If a participant withdraws before completion of the intervention this data will be solicited via telephone contact. Table 1 gives an example of how counts will be utilized throughout Aim 1 to describe the recruitment, enrollment, and adherence.

Table 2.

	Counts for feasibility	Use in analysis
Participants contacted	N	Total number of attempted recruits
Participants who enroll and consent	a	Recruitment rate: a/N
Participants who start Outreach-ER programming	b	Participation rate: b/N, compare to a/N
Participants who complete intervention (7+ visits)	c	Completion rate: c/b, used as main progression criteria Overall successful enrollment rate: c/N
Number who complete each intervention visit – k = 1, ..., 7	dk	Session specific completion rate: dk/b
Number who complete each questionnaire – m = 1,2	em	Questionnaire specific response rate: em/a and/or em/b if a ≠ b

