Aim 2: The completeness of the CES-D-10, ZBI-12, and PSS outcomes will be quantified by calculating the rate of CPs that respond to all items on each scale (CES-D-10: 10 items, ZBI: 12 items, PSS: 10 items) at each assessment. The rate of completion for both scales will be presented overall and stratified by questionnaire and by CP demographics. Preliminary efficacy analysis will utilize the total scores for the CES-D-10 (range: 0 to 30), ZBI (range: 0 to 48), and PSS (range: 0 to 40) calculated for all completed questionnaires. All outcomes will be summarized at both questionnaire timepoints using means and/or

medians, as appropriate. Change over the study timeframe (Q2-Q1) will be calculated for each CP and summarized for the sample. To evaluate change in efficacy outcomes, the pre and post scores of each instrument will be compared using paired t-tests. If there is no difference in outcomes, we expect Scorepre = Scorepost.

To determine the feasibility of collecting utilization outcomes, the proportion of enrolled CP/PLWDs who are eligible and consent to research access will be calculated. We will collect utilization data from the EHR including number of inpatient, outpatient, and ER visits for the PLWD in the 6 months before and the 3 months during as well as after participation. These counts will be summarized to describe the patterns in utilization associated with participating in the Outreach-ER programming.

Sensitivity analysis will remove those who do not complete the intervention (early withdrawal or <6 sessions). All analysis will be performed in SAS 9.4 and significance determined using a two-sided alpha of 0.05.

To explore the feasibility of obtaining online consent for research access to CP healthcare utilization records. healthcare utilization as an outcome in a full-scale ePCT. Any differences in CP/PLWD demographics between enrollees who opt-in and those who do not will be assessed.

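### Does an undefined 30-day readmission rate, with consent as the only stated feasibility measure for utilization, call for a change to the plan?

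*Combined protocol and SAP*

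**What the plan says.** Section 3 gives four utilization outcomes for the PLWD. Three are counts with periods of 6 months before and 3 months following the intervention. The fourth, the "30-day hospital readmission rate", has no period, index discharge or denominator. Sections 1.1 and 4.1 name readmissions again, as something to be described and reported.

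Section 9.1 does not mention readmission. For Aim 2 it states: "To determine the feasibility of collecting utilization outcomes, the proportion of enrolled CP/PLWDs who are eligible and consent to research access will be calculated". It then plans to take from the EHR the "number of inpatient, outpatient, and ER visits for the PLWD in the 6 months before", and extends the extract to 3 months during participation and to the time after it. These counts are to be summarized descriptively. A later, incomplete sentence in the same section refers to "healthcare utilization as an outcome in a full-scale ePCT".

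Under Aim 1, "Fidelity of the intervention will be assessed by describing CP attendance rates, length of intervention, and number of sessions". The table of feasibility counts makes completion (c/b) the main progression criterion. None of these items records time since discharge.

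On timing, Section 2.1 says: "A key feature of Outreach-ER is to reach out to PLWD and their families following an emergency room visit or hospitalization". Section 5.5 places the first call at 2 days to 2 weeks after discharge. Section 7.3.1 is headed "VISIT 3 (WITHIN 3 MONTHS OF DISCHARGE FROM HOSPITAL)". Entry under Section 5.1 is by emergency visit or by admission.

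**The concern.** A 30-day readmission rate needs a discharge to count from and a set of people at risk, and the plan names neither. The stated feasibility measure does not fill the gap. Consent to record access does not depend on how many PLWD were admitted, whether 30 days of follow-up exist, or when the intervention began.

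Two natural choices of index discharge run into difficulty. If it is the qualifying discharge, PLWD who entered on an emergency visit alone have no index admission, and the 30 days may be over before Visit 3. If it is a discharge in the 3-month period after the intervention, those near the end of that period may lack full follow-up.

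The pilot is meant to inform a larger study. The worry is that high consent would be taken to show that readmission works as an outcome when few PLWD could contribute to it, or when the window missed the intervention.

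**Working it through.** The plan states no figure for this outcome; its only sample-size table concerns CES-D-10. The checks below use its timings and N = 30.

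**Inputs.** 30 dyads (Section 9.2); first call on day 2 to 14 (Section 5.5); baseline within 10 days of Visit 1 (Section 7.2); Visit 3 up to about day 90 (Section 7.3.1); 10 ± 5 days between intervention visits (Section 7.3); written care plan at Visit 7 (Section 7.3.5); final visit 15 to 30 days after the last intervention visit (Section 7.4); completion 3 months after the final visit (Section 4.3); 21% of hospitalizations being unplanned 30-day readmissions or potentially avoidable care (Section 2.1).

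**1. What consent can show.** For 30 of 30, the exact lower limit is 0.025^(1/30) = 88.4%. This is the same whatever the number of index admissions.

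**2. Qualifying discharge as index.** With Visit 3 on day s, the part of the window left is max(0, 30 − s):

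| Visit 3 on day | Days left of 30 |
|---|---|
| 2 | 28 |
| 14 | 16 |
| 24 | 6 |
| 30 or later | 0 |

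Visit 7 falls at s + 40 on nominal spacing and s + 20 at the minimum. For s = 2 these are days 42 and 22. Day 2 is a bare bound, because the call, consent and baseline are all scheduled ahead of Visit 3. On this reading the overlap concern is correct.

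**3. Discharges in the 3-month post period.** Take 91 days with discharges spread evenly. If extraction stops at day 91, mean follow-up is (61 × 30 + 30 × 15)/91 = 25.1 of 30 days, a loss of about 16%. That cut-off is an assumption. If the 3 months run from the last intervention visit, Sections 7.4 and 4.3 leave 15 to 30 further days on study. With 15 extra days the mean is (76 × 30 + 15 × 22.5)/91 = 28.8 days, a loss of 4%. With 30 extra days nothing is lost.

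**4. Discharges during the intervention.** The Section 9.1 extract covers this period too. These discharges come after Visit 3, and the extract continues past the end of participation, so neither difficulty in steps 2 and 3 applies. At least one workable index therefore exists within the planned data.

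**5. Size.** Assume 10 to 30% of 30 PLWD are admitted after Visit 3 (the documents give no figure), so 3 to 9 are at risk. The 21% combines two categories and serves as an upper figure; half of it is shown for range.

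| Readmission risk | Expected events, n = 3 and 9 | Chance of none, (1 − p)^n |
|---|---|---|
| 21% | 0.63 and 1.89 | 49% and 12% |
| 10.5% | 0.32 and 0.94 | 72% and 37% |

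Exact 95% intervals for possible results: 1 of 6 gives 0.4 to 64.1%; 3 of 15 gives 4 to 48%. The rate is imprecise under any definition.

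**The case for a change.** The strongest case for a change is that Aim 2 exists to learn whether outcomes can be collected, and readmission is the first utilization outcome named in the synopsis. Visit counts do not link a readmission to an index discharge. Outreach soon after acute care is the program's key feature, yet no summary shows how soon it happens. A definition, a few counts and the discharge-to-visit intervals would need no new visits and at most 30 more days of extract.

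Three parts of this stand. The definition is missing. Time from discharge to Visit 3 would not be reported. Sections 3 and 9.1 also describe the utilization window differently, one covering only the period after the intervention and the other the period during it as well.

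The rest is weaker. Section 9.1 says a proportion will be calculated; it sets no cut-off and does not say that high consent establishes readmission as an outcome for a larger trial. That inference would be the reader's. The reference to a full-scale trial sits in a broken sentence next to text on care partners' own records, so little can rest on it. The planned inpatient counts would expose a near-empty denominator, and so would any rate reported with its numerator and denominator. The window difference does little harm: if the Section 9.1 extract is read as 3 months during and 3 months after, it contains the Section 3 period.

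**Conclusion.** No change follows. This is missing detail in a descriptive outcome. No test, sample-size calculation or progression decision uses the readmission rate; the main criterion is c/b, which the gap does not touch. No rule in the plan produces a wrong result. Whoever derives the rate must choose an index discharge, decide how emergency-only entrants count and state the denominator, and the planned extract allows a sensible choice, including discharges during the intervention.

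The size is small. With 3 to 9 PLWD at risk (an assumed range), fewer than two readmissions are expected even at the 21% upper figure. A tighter definition would make the number clearer but hardly more informative. The follow-up loss of about 16% depends on an assumed extraction cut-off and falls to 4% or nothing on another reading of the schedule. The overlap problem is real only if the qualifying discharge is the index.

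Summaries of time from discharge to Visit 3 would help readers of the pilot, but they are an optional addition.

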4 STUDY DESIGN

4.1 OVERALL DESIGN

This is a feasibility/pilot, prospective cohort study to determine how to implement and refine Outreach-ER intervention for a larger clinical study.

Aim 1

To assess the feasibility and acceptability of Outreach-ER. This aim will be accomplished by collecting detailed process data which will allow the assessment of registration, enrollment, retention, and adherence/fidelity to the program. This is an important step prior to moving forward with a larger trial. We will also utilize mixed methods approach, including semi-structured interviews and surveys to assess the acceptability and experience of participants.

Aim 2

To assess feasibility of collecting outcomes and explore the effectiveness of Outreach-ER. In care partners, we will evaluate the pre-post benefits of Outreach-ER to improve mood (Center for Epidemiologic Studies Depression Scale-10), reduce burden (Zarit Burden Interview-12), reduce stress (Perceived Stress Scale) and improve quality of life. We will describe and report healthcare utilization in PLWD, such as 30-day hospital readmissions and number of emergency room visits.

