5 STUDY POPULATION

5.1 INCLUSION CRITERIA

In order to be eligible to participate in this study, a dyad must meet all of the following criteria:

1. *PLWD with a recent Emergency department visit or admission at Regions Hospital or Methodist Hospital*

2. *Diagnosis of dementia based on ICD Codes in the medical record*
3. *Provides informed consent prior to participation*
4. *Must be able to read and speak English*
5. *PLWD Living at Home*
6. *Age >=18 years for PLWD and their care partner*

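### Utilization counts over unequal windows, with the qualifying hospital encounter left in the before-period, would show a fall even if Outreach-ER had no effect

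*Combined protocol and SAP*

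**What the plan says.** Section 3 lists three count measures for the PLWD: ED visits, ED visits leading to admission, and clinic visits. Each compares 6 months with 3 months; the first reads "Number of ED visits in 6 months before and 3-month period following the intervention". The only PLWD utilization item called a rate is 30-day readmission, which is outside this point.

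Section 9.1 (Aim 2) describes the data differently. It will extract the "number of inpatient, outpatient, and ER visits for the PLWD" "in the 6 months before and the 3 months during as well as after participation", and then: "These counts will be summarized to describe the patterns in utilization associated with participating in the Outreach-ER programming". It gives no person-time denominator. Section 4.1 sets the purpose: "We will describe and report healthcare utilization in PLWD, such as 30-day hospital readmissions and number of emergency room visits".

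Three other places fix where the qualifying encounter falls:

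- Section 5.1 requires a "PLWD with a recent Emergency department visit or admission at Regions Hospital or Methodist Hospital".
- Section 5.5: "Within a few days after discharge (2 days to 2 weeks) research staff will reach out to patients and their caregivers".
- Section 7.3.1 places the first intervention visit "WITHIN 3 MONTHS OF DISCHARGE FROM HOSPITAL".

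No section says whether this encounter belongs in the before-count.

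**The concern.** Two features of the plan push the counts down after the intervention whether or not the program works.

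The first is the qualifying encounter. Every PLWD enters because of an ED visit or admission, and that event sits in the before-window by design. The after-window has no matching event.

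The second is window length. On the Section 3 wording, 6 months of counts are set beside 3 months of counts.

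The two sections also describe different tables. Section 9.1 has a period during participation that Section 3 lacks, and it counts all inpatient visits where Section 3 counts admissions through the ED. The start of the after-period is not fixed either. It could be the last intervention visit (Visit 9 or 10) or Visit 11, which Section 7.4 places 15 to 30 days later. Section 4.3 ends participation 3 months after the final visit, which points to Visit 11, while Section 3 refers to the end of the intervention.

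Aim 2 includes exploring effectiveness, Section 2.1 presents PLWD utilization as something earlier studies did not examine, and Section 9.1 mentions utilization as an outcome for a full-scale trial. A spurious fall in ED and inpatient use would therefore feed into the next trial's planning.

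**Working it through.** The plan states no expected value for utilization, so there is no figure to reproduce. The check asks what the planned summary would show if the program did nothing.

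**Where the qualifying encounter falls.** Visit 3 is at most 3 months after discharge, and consent comes before Visit 3. Whether the before-period ends at consent or at Visit 3, the discharge lies within the preceding 3 months, inside a 6-month window. It cannot lie after the intervention.

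**Inputs**
- Windows: 6 months before and 3 months after (Section 3), or 6 before, 3 during and 3 after (one reading of Section 9.1).
- N = 30 PLWD (Section 9.2 plans up to 30 dyads).
- L = background events per person-month, constant. The documents give none; 0.1 to 0.5 is assumed.
- p = share of PLWD whose qualifying encounter counts in the measure. It is 0 for clinic visits and at most 1 for any single measure.

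**What needs no assumed rate level**
- Clinic visits, Section 3 windows: 3L / 6L = 0.50, a 50% fall at any constant L.
- Section 9.1 categories: each qualifying encounter is an ER visit, an inpatient visit or both. Across those two measures it adds at least 30 events before and 0 after. Over 30 × 6 = 180 person-months that is at least 30/180 = 0.167 events per person-month. Since the two shares sum to at least 1, at least one of the two measures has p of 0.5 or more.

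**Raw counts, Section 3 windows.** Before = 6L + p, after = 3L, apparent fall = 1 − 3L/(6L + p).

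**Monthly rates, or the during and after periods pooled to 6 months, with the qualifying encounter kept.** Apparent fall = p/(6L + p).

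| p | L per month | Before (6 months) | After (3 months) | Fall, raw counts | Fall, rates or pooled |
|---|---|---|---|---|---|
| 0 | any | 6L | 3L | 50% | 0% |
| 0.5 | 0.1 | 1.10 | 0.30 | 72.7% | 45.5% |
| 0.5 | 0.2 | 1.70 | 0.60 | 64.7% | 29.4% |
| 0.5 | 0.5 | 3.50 | 1.50 | 57.1% | 14.3% |
| 1 | 0.1 | 1.60 | 0.30 | 81% | 62.5% |
| 1 | 0.2 | 2.20 | 0.60 | 72.7% | 45.5% |
| 1 | 0.5 | 4.00 | 1.50 | 62.5% | 25.0% |

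At a lower assumed rate of 0.5 per person-year with p = 1, the before-count is 1.25 and the after-count 0.125. The falls are then 90% raw and 80% as rates.

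**Three-period table for 30 PLWD at L = 0.2.** The before/during/after totals are 36/18/18 at p = 0, 51/18/18 at p = 0.5, and 66/18/18 at p = 1.

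**Both corrections together.** With rates and the qualifying encounter excluded, the ratio is (3L/3)/(6L/6) = 1.00 at any constant L.

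**Start of the after-period.** The 15 to 30 days between the two possible starts are 15/91 = 16% to 30/91 = 33% of a 91-day window.

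**The case against.** The strongest reply is that no before/after contrast is planned for the PLWD. Section 4.1 keeps its pre-post language for care partners. Section 9.1 confines the paired t-tests to the care-partner scales, and it introduces utilization as a question of whether the data can be collected. The main progression criterion is the completion rate. All of this is correct, and it limits the severity: no type I error is inflated and no decision rule is affected. It does not remove the problem, because the counts are meant to describe patterns associated with participation, and a reader will compare the periods.

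The 6-versus-3 imbalance arises only on the Section 3 reading. If Section 9.1 means 3 months during plus 3 months after, pooled, it disappears. A reader who sees the window lengths can also correct for it. Both points stand. Neither helps with the qualifying encounter, which survives rescaling and cannot be subtracted unless it is reported.

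The percentages beyond 50% rest on an assumed rate and share, and the figure of 30 events adds two measures that the plan lists separately. That also stands. The direction does not depend on either assumption whenever p is above 0. As a number, the qualifying encounter outweighs the window effect only when 6L < p, that is, below 0.167 events per month at p = 1 or 0.083 at p = 0.5.

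Finally, Section 4.3 goes some way towards fixing the follow-up anchor. It does not settle when the after-count begins, because Section 3 ties that to the intervention.

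**Conclusion.** The concern holds. Followed as written, the plan gives a utilization summary tilted towards benefit. With no effect and a constant rate:

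- **Clinic visits:** 50% lower on the Section 3 windows, and no bias with rates or pooled 6-month periods.
- **ED and inpatient measures, raw counts on the Section 3 windows:** 57% to 73% lower at p = 0.5 and 63% to 81% lower at p = 1.
- **ED and inpatient measures, rates or pooled periods with the qualifying encounter kept:** 14% to 45% lower at p = 0.5 and 25% to 63% lower at p = 1.

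The ED and inpatient ranges assume 0.1 to 0.5 events per month. The Section 3 categories can also miss the encounter: a direct admission is neither an ED visit nor an ED-to-hospital admission. Because the analysis is descriptive, this should be fixed, but it does not threaten the study's main feasibility results.

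**What to change.** 1. Report each measure as events per person-month observed in each period, so that unequal windows and early withdrawal are both handled.
2. Exclude the qualifying encounter from the before-count of every measure it belongs to, and report it on its own line.
3. Use one set of before, during and after windows in Sections 3 and 9.1, with stated start and end points. Say whether the after-period starts at the last intervention visit or at Visit 11, consistently with Section 4.3.
4. Use one set of visit categories in both sections: either all inpatient visits, or admissions through the ED, or both, each defined.
5. State with the results that regression to the mean remains. People enrolled just after an acute episode may use less care later without any program, and a single-arm study cannot separate the two.

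The cost is some wording and minor programming on EHR data already due to be extracted. No new data are needed. The apparent reduction in ED and inpatient use will look smaller than under the current plan.
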